#### 6.4. STATISTICAL TESTS

The default significance level will be 5% 2-sided; confidence intervals will be 95% (2-sided), unless otherwise specified in the description of the analyses.

#### 6.5. COMMON CALCULATIONS

For quantitative measurements, the following formulates will be used if applicable:

- Change from baseline =Test Value at Visit X Baseline Value
- Percentage change from Baseline (%) = (Test Value at Visit X Baseline Value) / Baseline Value × 100

#### 6.6. SOFTWARE VERSION

All analyses will be conducted using SAS version 9.4 or higher.

#### 7. STATISTICAL CONSIDERATIONS

# 7.1. ADJUSTMENTS FOR COVARIATES AND FACTORS TO BE INCLUDED IN ANALYSES

No adjustment for covariates and factors will be used in the analyses.

#### 7.2. MULTICENTER STUDIES

This study will be conducted by multiple investigators at multiple centres. Because a small

 $Document: \underline{\label{locality} Nieedc-vnac01\\Biosdata\\Genexine\\GX-188E\\GYA02599\\Biostatistics\\Documentation\\SAP}$ 

Author: [name] Version Number: 1.1

Version Date: 05Sep2022

Template No: CS\_TP\_BS016 Revision 6 Reference: CS\_WI\_BS005

Effective Date: 02Dec2019

Page 19 of 48

PROTOCOL GX-188E-005

Analysis Plan

number of patients are expected at each center, data from all centers will be pooled and no center effect will be investigated.

#### 7.3. MISSING DATA

Generally, missing data will not be imputed.

For death date, if year and month of death date are known but the day of date is unknown, day will be imputed as 1. For example, if a patient is reported to die on Dec 2016, the death date will be imputed as 01Dec 2016.

Imputed dates will NOT be presented in the listings.

Partial dates of adverse events and prior/concomitant medication will be handled as described in Appendix 2.

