# 16.13 Long-Term Follow-Up

Patients will enter into the long-term follow-up phase of the study after the EOS visit to obtain survival data. Survival data may be obtained either by clinic visit or by remote communication (e.g., telephone call or email) or hospital medical records. Sites must follow up with patients approximately every 4 months for up to 1 year to obtain the following data:

- Survival status: Is the patient still living? (Yes or No)
  - o If "No", what was the approximate date of death?
- Has the patient received any subsequent active anti-cancer treatment (this does not include palliative measures)? (Yes or No)
  - o If "Yes", what treatments has the patient received?

Family members, primary care giver, public records, or primary treating oncologist/oncologist's office may confirm a patient's death.

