#### OS

Overall survival is defined as the time from treatment initiation until death from any cause. Median OS time (months) is the timepoint at which the probability of survival equals 50% in the efficacy evaluable population. Patients developing no event will be censored on the last known survival date. Patients providing no follow-up information will be censored on the day of first dosing. Kaplan-Meier method will be used to estimate median OS and the corresponding 95% CI. Kaplan-Meier curves will be constructed to provide a visual presentation of the OS rate change with time.

6-month OS rate is the proportion of efficacy evaluable patients who are alive 6 months after treatment initiation. The OS rate and 95% CI at 6 months will also be summarized.

OS will be displayed for Part A, Part B and Part C.

Waterfall, Spider, Swim-lane and forest Plots

A waterfall plot will be prepared to visually present the best percentage change from baseline in sum of diameters in target lesions for each patient grouped by PD-L1 status, HPV type, and histologic type.

A Spider Plot will be used to visualize changes in sum of diameters in target lesions with best overall response by BICR according to RECIST 1.1. With a Spider Plot, post-baseline measurements are compared to the baseline. Thus, the data plotted is the percent change from baseline over the period of patient evaluation. Each leg of the "spider" represents a unique patient.

Swim-lane Plot for Tumor Response will be presented to show tumor assessment by at each

Document: \\ieedc-vnac01\Biosdata\Genexine\GX-188E\GYA02599\Biostatistics\Documentation\SAP

Author: [name] Version Number: 1.1

Version Date: 05Sep2022

Template No: CS\_TP\_BS016 Revision 6 Reference: CS\_WI\_BS005

PROTOCOL GX-188E-005

Analysis Plan Page 34 of 48

visit. Specifically, the Swim-lane plot will show total time to tumor response, whether the response was complete or partial, when the response started/ended and censoring information of the patient grouped by PD-L1 status, HPV type, and Histologic type.

These plots will be displayed only for Part C.

In Part C, a forest plot will be used to display BICR Assessed BORR according to RECIST v1.1 across subgroups.

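### A death date with an unknown day is set to the first of the month with no floor at the last known alive date, so a death can be dated before the patient's own last scan, dose or contact (minor)

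*SAP*

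**What the plan says.** SAP 7.3 starts from a general position: "Generally, missing data will not be imputed". It makes an exception for death, when the year and month are known but "the day of date is unknown, day will be imputed as 1". Its worked example is that "if a patient is reported to die on Dec 2016, the death date will be imputed as 01Dec 2016". No condition refers to the last visit, dose, scan or contact. The same section adds that "Imputed dates will NOT be presented in the listings".

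No other section supplies the missing condition. SAP Appendix 2 covers partial dates for adverse events and medications only. In SAP 15.2, "Overall survival is defined as the time from treatment initiation until death from any cause", and the last date known alive is used only for patients without an event: "Patients developing no event will be censored on the last known survival date". The protocol has no partial-date rule.

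On data collection, Protocol 16.13 has sites follow survival about every 4 months for up to 1 year, by visit, remote contact or records. If the patient has died, the question is "what was the approximate date of death".

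**The concern.** Applied as written, the rule can contradict dates already in the database. It can place a death before a scan that was read, a dose that was given or a contact that was logged. The imputed value is kept out of the listings, so a listing review would not show the conflict.

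The error also has one direction. Day 1 is the earliest possible day, so every affected survival time is shortened or left unchanged. This reaches four results:

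- **Median OS**, directly.
- **The 6-month OS rate**, where a patient known to be alive at 6 months could be counted as dead.
- **PFS**, when death is the event. The imputed death can precede the last progression-free scan. It can also change event status under the 126-day missed-assessment rule of SAP 15.2. For example, a death on the 10th of a month, 130 days after the last evaluable scan, is censored on its true date. Imputed to the 1st it falls 130 - 9 = 121 days after the scan and becomes an event.
- **Follow-up time**. SAP 9 takes it to the latest of death, last contact and similar dates, so a deceased patient could have follow-up longer than her OS time.

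**Working it through.** **Inputs from the documents**
- Day of death set to 1 when only the day is missing (SAP 7.3).
- Contacts about every 3 weeks on treatment (Protocol 16.11), taken as 21 days, and about every 4 months in long-term follow-up (Protocol 16.13), taken as 122 days.
- At least 45 days on treatment for most routes into the efficacy evaluable population (SAP 5.4).

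**Assumptions, not in the documents**
- The true day of death is equally likely to be any day.
- The gap from last contact to death is uniform over the contact interval.
- Survival is exponential with a median of 6, 12 or 18 months.
- The share of deaths with a missing day is 5% to 100%.

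**1. The SAP's own example.** December has 31 days, so 01Dec2016 is 0 to 30 days before the true date, on average (31 - 1)/2 = 15 days.

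**2. Mean shift per affected death.** In a month of L days the mean shift is (L - 1)/2: 14.5 days for L = 30 and 15 for L = 31. Over all 1,461 days of 2019-2022 it is 14.73 days, or 14.73/30.4375 = 0.48 month. The maximum is 30 days.

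**3. How often the imputed death precedes last contact.** This happens when the gap from last contact to death is shorter than the shift.
- 3-week contacts, simulated: about 64% of affected deaths. Check for a 31-day month: the mean of min(shift, 21)/21 over shifts 0 to 30 is (231 + 189)/(21 × 31) = 420/651 = 0.645.
- 4-month contacts: 14.73/122 = 0.12, which matches the simulated 12% when everyone survives at least 45 days. Without that minimum it is 14% to 17%, because early deaths have first dose as their last contact.

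**4. Effect on the reported estimates** (simulated, 12-month median, no censoring):

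| Share of deaths with day missing | Median OS shortened by | 6-month OS rate lowered by |
|---|---|---|
| 5% | 1 day | 0.1 points |
| 10% | 2 days | 0.2 points |
| 25% | 3 days | 0.5 points |
| 50% | 7 days | 1.0 points |
| 100% | 15 days | 1.9 points |

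The shift in the median is roughly the share times 14.7 days.

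**5. Can the imputed death precede first dose?** Day 45 of treatment is 44 days after first dose. The largest shift is 30 days, so the earliest imputed death is 44 - 30 = 14 days after first dose. A check over start dates also gave a minimum of 14. With no minimum treatment time, about 2% to 5% of affected deaths would fall before first dose.

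**6. Candidate fixes, mean error per affected death:**

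| Rule | 3-week contacts | 4-month contacts |
|---|---|---|
| Day 1 (as in the SAP) | -14.7 days | -14.7 days |
| Day 1 with floor at last known alive | about -7.5 days | about -13 days |
| Day 15 with the same floor | about +0.5 day | about -0.5 day |

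The floor removes the impossible dates but only part of the bias. Day 15 with the floor removes nearly all of it.

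**The case against.** The strongest reply is that day 1 is a pre-specified and conservative convention, applied to a descriptive secondary endpoint in a single-arm trial. That stands. Day 1 versus day 15 is partly a matter of convention, and the bias cannot flatter the regimen. What the reply does not cover is the missing order check: no convention justifies a death dated before a documented scan.

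Frequency is also open to challenge. An approximate date may still include a day, in which case nothing is imputed. Protocol 16.13 also allows hospital records, public records, family and the treating oncologist as sources. Long-term follow-up is where missing days are most plausible, and there a contact in the month of death is uncommon (12% to 17% above). On treatment, where the conflict would be common (64%), serious adverse events are reported within 24 hours (Protocol 20.7), so an unknown day is less likely. All of this stands, and it is why the point is minor.

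Three stronger readings are tempting, and the documents do not support them:
- **Deaths will be dated before first dose.** SAP 8 and 15.2 place OS and PFS in the efficacy evaluable population, and its 45-day minimum excludes this (step 5). The remaining route is early discontinuation for toxicity, which SAP 5.4 identifies by dose-limiting toxicity, followed by death in the calendar month of first dose. Inclusion also requires a life expectancy of at least 6 months. The possibility is remote.
- **Every incomplete death date goes to the first of the month.** The rule applies only when the day alone is missing. For an unknown month the SAP has no specific rule.
- **Any contact in the month of death makes the imputed date impossible.** A contact on the 1st gives an equal date, not an earlier one.

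The reach into PFS is limited too. A death after documented progression does not change PFS, and a death after new anti-cancer therapy is censored. Duration of response is less clear: the protocol ends it at progression, while the SAP's censoring text also mentions death.

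**Conclusion.** The gap is real and of minor priority. SAP 7.3 can date a death before the patient's last scan, dose or contact in the same month, and no other section prevents it. Each affected OS time, and each affected PFS time that ends in death, is shortened by 0 to 30 days, about 15 on average.

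The effect on median OS is probably a few days: about 1 to 3 if 5% to 25% of deaths lack a day and the true median is 12 months. Both figures are assumptions, because the documents give neither. A reader might infer that the OS results would be materially distorted. The arithmetic supports that only if most deaths had no recorded day, and nothing in the documents suggests it. The direction is conservative, and ORR24, the endpoint that carries the hypothesis test, does not use the death date.

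**What to change.** Amend SAP 7.3 so that an imputed death date is never earlier than the last known alive date, meaning the latest of the last visit, dose, scan or contact. Cap it at the last day of the reported month and at the data cut-off. If the last known alive date is later than the reported month of death, raise a data query instead of imputing.

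Preferably replace day 1 with day 15 under the same floor. This is optional: the floor cures the impossible dates, and day 15 removes nearly all of the remaining bias. The same edit could add a rule for an unknown month and an imputation flag beside the death date in the listings.

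The cost is one or two SAP sentences and a line of derivation code, agreed before database lock. It needs no new data and no change to trial conduct.

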## 7.4. MULTIPLE COMPARISONS/ MULTIPLICITY

No multiple comparisons and multiplicity adjustment will be performed.

#### 7.5. EXAMINATION OF SUBGROUPS

- (1) In Part C, ORR24, BORR and DCR will be assessed and described in the following subgroups:
- Age
  - o Less than 50 years
  - o ≥50 to < 65
  - o Equal to or more than 65 years
- HPV type
  - o HPV-16
  - o HPV-18 or both
- Histology type
  - o Squamous cell carcinoma
  - o Adenocarcinoma

Document: \\ieedc-vnac01\Biosdata\Genexine\GX-188E\GYA02599\Biostatistics\Documentation\SAP

Author: [name] Version Number: 1.1

Version Date: 05Sep2022

Template No: CS\_TP\_BS016 Revision 6 Reference: CS\_WI\_BS005

Effective Date: 02Dec2019

PROTOCOL GX-188E-005

Analysis Plan

Page 20 of 48

Prior bevacizumab o Yes o No

**■IOVIA** 

 Eastern Cooperative Oncology Group (ECOG) Performance Status at baseline o 0

o 1

 PD-L1 status at baseline o Positive (≥1 CPS)
 o Negative (<1 CPS)

In Part C, DOR, TTR, PFS and OS by PD-L1 status, HPV type, and Histologic type subgroups will be summarized. Kaplan-Meier curve of BICR/investigator-assessed PFS according to RECIST v1.1 stratified by PD-L1 result, or HPV type, or Histologic type will be displayed. Kaplan-Meier curve of overall survival stratified by PD-L1 result or HPV type, or Histologic type will also be displayed.

- (2) Using pain killer or local anaesthetic as a premedication to control the pain may affect Pain assessments. A subset of the safety population (who used pain killer or local anaesthetic to control the pain before GX-188E administration using electroporator) will be used for sensitivity analysis. The following summaries will be made based on the subset of safety population.
- Pain Assessments Summary

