A patient who meets all of the inclusion criteria may enter the study. Screen failures will be reported into the Screen Failures Log.

# 16.2 Week 1 Day 1

At the Week 1 Day 1 visit, patients will return to the clinic for the first administration of GX-188E and P.

Patients will undergo the following procedures on Week 1 Day 1:

- 1. AE monitoring
- 2. Recording of concomitant medications
- 3. Vital signs and weight
- 4. Symptom-directed physical exam

- 5. Clinical laboratory evaluation (hematology, serum chemistry, urinalysis). The laboratory tests may not be performed repately if the screening tests were performed within 7 days of Week 1 Day 1 and the clinically significant changes for the results were not suspected.
- 6. Research blood collection. This sample must be obtained prior to the first dose of GX-188E and pembrolizumab.
- 7. Pain Assessment. Within 30 minutes before and 5 minutes (± 2 minutes) after GX-188E administration, pain score in association with the electroporation (EP) procedure should be reported.
- 8. Administration of GX-188E at both right and left deltoid muscles
- 9. Administration of pembrolizumab. For the purposes of this study, pembrolizumab should be administered *after* the GX-188E vaccination on all days in which patients are scheduled to receive both.

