#### 20.1.4 Pain Assessment

On each GX-188E vaccination day, Pain Assessment Monitoring will be performed within 30 minutes before and 5 minutes (± 2 minutes) after the vaccination procedure using a 0-10 numeric pain rating scale (Figure 4).

[figure not shown]

Figure 4. Numeric Pain Rating Scale

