#### 8. OUTPUT PRESENTATIONS

Appendix 1 shows conventions for presentation of data in outputs.

The mock up TFLs shell provided with this SAP describe the presentations for this study and therefore the format and content of the summary tables, figures, and listings to be provided by IQVIA Biostatistics.

Summary statistics for continuous variables will include the mean, standard deviation, median, interquartile range, and range (minimum/maximum). Categorical variables will be presented as frequency counts and percentages, and time-to-event variables will be summarized with number

Document: \(\)\ieedc-vnac01\\Biosdata\\Genexine\\GX-188E\\GYA02599\\Biostatistics\\Documentation\\SAP\)

Author: [name] Version Number: 1.1

Version Date: 05Sep2022

Template No: CS\_TP\_BS016 Revision 6 Reference: CS\_WI\_BS005

Effective Date: 02Dec2019

Analysis Plan

Genexine

PROTOCOL GX-188E-005

Page 21 of 48

of non-missing observations, median time, and survival probability using Kaplan-Meier method if applicable. Kaplan Meier plot will also be provided.

The data will be tabulated and analyzed with respect to patient enrollment and disposition, demographic and baseline characteristics, prior and concomitant medications, efficacy, and safety results. The efficacy analysis will be conducted on the Efficacy Evaluable Population, and the safety analysis will be performed on the Safety Population.

Data listings will be created to support each table and to present all data collected.

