#### 16. SAFETY OUTCOMES

Safety variables to be analyzed are AEs, laboratory test results (e.g., hematology, coagulation, serum chemistry, thyroid function tests, and urinalysis), vital signs and others.

All outputs for safety outcomes will be based on the safety population. The results will be presented for Part A, Part B Part C and overall except for DLT.

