#### 16.7. OTHER EXAMINATIONS

ECOG of Performance Status will be reported for the study. The following summaries will be provided for the ECOG data.

- Worst post-baseline result
- Baseline and post-baseline by visit summary table

 $Document: \underline{\label{locality} Nieedc-vnac01\\Biosdata\\Genexine\\GX-188E\\GYA02599\\Biostatistics\\Documentation\\SAParticles \\Documentation\\SAParticles \\Documentation\\SAParticles \\Documentation\\SAParticles \\Documentation\\SAParticles \\Documentation\\SAParticles \\Documentation\\SAParticles \\Documentation\\SAParticles \\SAParticles \\SAParti$ 

Author: [name] Version Number: 1.1

Version Date: 05Sep2022

Template No: CS\_TP\_BS016 Revision 6 Reference: CS\_WI\_BS005

Effective Date: 02Dec2019

PROTOCOL GX-188E-005

Analysis Plan Page 42 of 48

• Shift from baseline to worst post-baseline table

Individual ECOG data will be listed.

Device malfunction information collected on "Device Malfunction" page of CRF will be listed.

Tumor Biopsy Sample collected on "Tumor Biopsy Sample" page of CRF will be listed.

Pregnancy test information will be listed.

Serology results will be listed.

Pain assessment information will be summarized and listed.

A listing will be provided for patients whose trial participation are impacted by COVID-19, including patient number and site number together with a description of the impact. These protocol deviations are documented in IQVIA clinical trial management system,

Research blood collection will be listed.

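### The pain sensitivity summary in SAP 7.5(2) covers only premedicated patients, so no planned summary shows pain at vaccinations given without premedication

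*SAP*

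**What the plan says.** Protocol 16.2 and the later vaccination visits ask that a "pain score in association with the electroporation (EP) procedure should be reported". Protocol 20.1.4 sets the timing: "On each GX-188E vaccination day, Pain Assessment Monitoring will be performed within 30 minutes before and 5 minutes" (tolerance 2 minutes) after the procedure, on a 0-10 scale. There are six planned vaccination days and an optional one at Week 46, so each patient contributes repeated scores.

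SAP 7.5(2) gives the reason for a sensitivity analysis: "Using pain killer or local anaesthetic as a premedication to control the pain may affect Pain assessments". The subset is the patients "who used pain killer or local anaesthetic to control the pain before GX-188E administration using electroporator". On the output, the SAP says "The following summaries will be made based on the subset of safety population", and the one item listed is a pain assessments summary.

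The main pain output is in SAP 16.7: "Pain assessment information will be summarized and listed". SAP 16 fixes its population: "All outputs for safety outcomes will be based on the safety population". Neither section splits pain by premedication.

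**The concern.** If the worry is that premedication alters the score, the informative comparison sets scores taken without premedication against scores taken with it. The plan gives one table that mixes the two and one restricted to the premedicated patients. The group that would show pain without premedication has no table.

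What is at stake is how the electroporation pain result is read. Protocol 15.1 generally permits supportive medication, and I found no protocol rule that standardises premedication before electroporation, so use may vary between patients and visits. If the subset table resembles the main table, a reader could take the label of sensitivity analysis to mean that the pain result is robust to premedication. That inference would not follow.

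**Working it through.** The plan gives no figure to reproduce. The check sets the sections side by side and then uses a small identity.

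**1. Which groups get a summary**

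| Group | Planned pain summary | Source |
|---|---|---|
| All safety-population patients | Yes | SAP 16, 16.7 |
| Patients who used premedication | Yes | SAP 7.5(2) |
| Patients or visits without premedication | None named | none |

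**2. What each summary estimates.** Define:
- f = share premedicated
- d = reduction in score caused by premedication
- U = mean score in the non-premedicated group
- s = amount by which the premedicated group would score above U if it had no premedication (selection)

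The means are then:
- non-premedicated group: U
- premedicated subset: U + s - d
- pooled summary: U + f(s - d)
- everyone, had nobody been premedicated: U + fs

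Differences from that last value:
- pooled: -fd
- premedicated subset: (1 - f)s - d
- non-premedicated group: -fs

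**3. No selection (s = 0).** The differences are -fd, -d and 0. The documents give neither d nor f. Purely as an illustration, take d = 2 points:

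| f (assumed) | Pooled, -fd | Premedicated subset, -d | Non-premedicated |
|---|---|---|---|
| 0.2 | -0.4 | -2.0 | 0 |
| 0.5 | -1.0 | -2.0 | 0 |
| 0.8 | -1.6 | -2.0 | 0 |

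In this case the planned subset lies further from premedication-free pain than the table it is meant to check, for any d > 0 and f < 1.

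**4. With selection (s = d).** Suppose patients who hurt more are the ones premedicated, and s equals d. The subset difference is (1 - f)d - d = -fd, the pooled difference is -fd and the non-premedicated difference is -fd. All three summaries agree, although premedication has an effect. So neither the direction of bias nor a clean comparator can be assumed. Both groups need to be shown, with that caveat.

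**5. Can the missing summary be recovered?** With N and mean M for all, and n and mean m for the subset, the complement's mean is (N x M - n x m) / (N - n). The median and interquartile range, which SAP 8 also reports, cannot be recovered this way.

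**6. Unit of analysis.** The subset is defined by patient and the score is taken by visit. The SAP does not say how to class a patient premedicated at some vaccinations only. If she counts as a user, her unpremedicated visits enter the subset, and the back-calculated mean in step 5 then describes never-premedicated patients, not unpremedicated visits.

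**The case against.** The strongest reply is that the subset is not read alone. Set beside the pooled table, it shows indirectly whether premedicated patients score differently, and the mean of the rest can be back-calculated. SAP 8 adds that "Data listings will be created to support each table and to present all data collected". This stands in part: the planned table has descriptive value and is not useless. But the contrast is indirect, recovers no median or interquartile range, and a listing is not an analysis.

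It can also be said that neither document names premedication-free pain as the target, and that pain as experienced, with premedication where given, is a legitimate safety description. That is fair for the main table. It does not explain a sensitivity analysis whose stated reason is the influence of premedication.

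Two further cautions stand. The table shells mentioned in SAP 8 are not among the documents available here and may show both groups. The wording may also be a slip for patients who did not use premedication, which would make this a short correction.

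A reader might go further and infer that the planned table will show the most masked scores, too low by some number of points, on the trial's main measure of device tolerability. The documents do not support that. The SAP says only that premedication may affect the score. No effect size or rate of use is given. Selection can offset or reverse the difference. Pain sits under other examinations in SAP 16.7 and is not a named primary or secondary endpoint.

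**Conclusion.** The point holds in a limited form. As written, the sensitivity analysis does not directly address its own stated concern, because no summary named in the SAP text shows pain at vaccinations without premedication, and because the subset is defined by patient while the score is taken by visit.

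The size cannot be stated from the documents. The figures in the working rest on an assumed d and f and, in the table, on no selection, so they illustrate the logic and do not estimate a bias. The consequence is confined to interpreting procedure pain. ORR24, the sample size and the other efficacy analyses are untouched. Severity is minor, but the correction is cheap and changes what the table can show.

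**What to change.** In SAP 7.5(2), replace the single subset with a side-by-side summary of vaccination visits with and without analgesic or local anaesthetic premedication, giving the pre-procedure score, the post-procedure score and the change. If the intended subset was patients who did not use premedication, correct the wording, and preferably still define the groups by visit.

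Classify each visit from both prior and concomitant medication records, using dates and indication, and time where recorded. Two details matter:
- SAP 12.1 and Appendix 2 class a medication stopped on the day of first study treatment as prior only. A filter on concomitant records would therefore miss single-day premedication at Week 1 Day 1.
- SAP 12.1 lists start and end dates but mentions no clock times. Dates alone cannot separate a drug given before the procedure from one given afterwards on the same day. State how ambiguous visits are handled and report how many there are.

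Add a sentence that premedication was not randomised, so the comparison is descriptive. The cost is a short SAP edit, a small amount of programming and some visits that may stay unclassifiable. No new data collection appears to be needed.
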